## 1 PURPOSE

We recently completed Phase A and Phase B of our Feasibility Study of the LUM Imaging System (NCI funding 5R21CA173762-02): Feasibility clinical study of real-time tumor bed imaging in breast cancer patients. Based on the experience gained from this work, we propose to expand the Feasibility Study into multiple institutions (Phase C) with the main goal of standardizing the training for surgeons and clinical staff and to collect additional imaging and pathology data to further refine and verify the tumor detection algorithm. Phase C of the Feasibility Study will be expansion to a maximum of 20 sites, with each site having approximately 1-3 surgeons participating. The study may include up to 250 patients. This study remains non-randomized and open label.

## 2 SUMMARY OF OBJECTIVES

- Collect data to refine and verify the tumor detection algorithm
- Complete hands-on training of the surgeons and clinical staff that will be participating in the pivotal study to evaluate the efficacy and safety of the LUM Imaging System in breast cancer surgeries
- Identify and address any site-specific or user-specific issues for using the LUM Imaging System in breast cancer surgeries
- Collect safety and efficacy data

## 3 BACKGROUND

### 3.1 Study disease

For breast cancer lumpectomies, the presence of residual cancer cells left in the tumor bed after initial resection is inferred by post-operative margin assessment of the resected tissue by a pathologist. For invasive carcinoma, a positive margin is defined as having tumor present at the inked side of the outermost surface of the lumpectomy specimen [1]. When ductal carcinoma in situ (DCIS) is present, a positive margin occurs when DCIS is found within 2 mm from the inked surface [2]. Positive lumpectomy margins are the most important risk factor for local recurrence of breast cancer [1-5] and dictate that a second surgical procedure be performed to obtain tumor-free margins. The rates of close or positive margins have been reported between 17 to 59% [6-10]. Among the more than 318,000 women expected to be diagnosed with breast cancer in the US in 2017, approximately 200,000 will undergo lumpectomy and approximately a third will require additional surgery for positive margins. Thus, a diagnosis of positive margins indicates that additional treatments are needed. This places a heavy burden on patients and adds significant cost to the healthcare system.

### 3.2 Rationale

Achieving negative margins during tumor excision is critical to assure that all or most of the cancer has been removed from the patient. Current standard of care dictates that tissue removed during surgery is analyzed post-operatively for tumor histology and margin assessment by a pathologist as described above. This procedure is time consuming, often requiring 7-10 days of pathology

LUMICELL CONFIDENTIAL

This document is confidential. Do not disclose or use except as authorized.

testing after the operation before margin status is known. In addition, this process is prone to sampling errors, as only a finite number of tissue slices can be examined, meaning that only a small fraction of the lumpectomy margin surface is assessed, < 1% of lumpectomy surface area by some estimates. Thus, a safe method to directly assess the entire tumor bed intraoperatively and identify residual microscopic disease for immediate resection intraoperatively would be highly beneficial for patients.

Lumicell has developed the LUM Imaging System, which consists of a fluorescence-based imaging agent (LUM015), a hand-held, wide-field detector (LUM Imaging Device) that can image the lumpectomy cavity in seconds, and a tumor detection algorithm that highlights regions suspected to contain cancer and displays them on a computer monitor. The LUM Imaging system is intended to be used to scan the lumpectomy cavity walls intraoperatively after the resection of the main lumpectomy specimen.

The Lumicell Imaging System may enable surgeons to achieve negative margins during the initial surgery and eliminate or reduce the need for re-excision surgeries when compared with current standard of care procedures. Lumicell's system images the entire lumpectomy cavity surface *in vivo*, overcoming tissue handling and sampling limitations of standard pathology analysis of resected tissue. The LUM Imaging System provides real-time feedback to the surgeon about the status of the lumpectomy cavity walls, and does not require patient immobilization; hence, the system may not significantly impact surgical workflow.

The LUM Imaging System has been tested in a two-phases of the Feasibility Study at the Massachusetts General Hospital. Fifteen patients in Phase A and 45 patients in Phase B were included in the study. The results indicate zero false negatives in the margin cavity walls and avoidance of two second surgeries based on the detection of positive signal with the LUM Imaging Device. These results are presented in the Phase B report.

This experience showed that user related issues are not easily identified until the surgeon uses the system in the clinical setting. No amount of "dry runs" outside the operating room reveal the important issues that arise during surgery; for example, optimizing a surgeon's approach for keeping the hand-held unit in contact with the tissue, thorough scanning of the cavity walls, and co-location of the image with the additional shaved margin tissue to be removed. Therefore, we believe that it is critical to introduce the LUM Imaging System into additional clinical sites and train the clinical staff prior to the pivotal study.

## 4 PRODUCT DESCRIPTION

### 4.1 Intended use

The LUM Imaging System is a combination product consisting of the LUM015 imaging agent and the LUM Imaging Device. LUM015 is administered to the patient via intravenous injection 4 ± 2 hours prior to surgery. The LUM Imaging Device is intended for use *in vivo* following the excision of the main lumpectomy specimen to potentially help determine whether cancer remains in the lumpectomy cavity walls based on the tissue fluorescence signals.

LUMICELL CONFIDENTIAL

[figure not shown]
This document is confidential. Do not disclose or use except as authorized.

## 4.2 Indications for use

The LUM Imaging System is indicated for use in patients undergoing a breast conserving surgery (lumpectomy) to remove breast cancer. The LUM Imaging System is intended to be used whenever breast tissue is removed, histopathology evaluation of the tissue is the standard of care and/or it is essential that the tissue margins be examined for completeness of removal using standard surgical procedures. The LUM Imaging System is used *in vivo* following the excision of the main lumpectomy specimen to assist in locating residual abnormal tissue, therefore, facilitating tumor resection and reducing the risk for cancer-positive margins in the resected tissue.

## 4.3 LUM015 imaging agent

Lumicell engineered LUM015, a fluorescence-based imaging agent that accumulates within and around cells. In regions enriched with cathepsin enzymes, such as cancer cells, LUM015 is altered to produce a fluorescent signal. In its nominal state, the fluorescence of LUM015 is suppressed by an internal quencher molecule (QSY21). The presence of cathepsin enzymes is not fully confined to cancer cells; hence, data from this study will help determine the cancer localization properties of LUM015. Once cathepsin enzymes cleave LUM015 at its amino acid backbone, the quencher is released and the fluorescent dye (Cy5) in LUM015 emits detectable fluorescence (**Figure 1**). The absorption and emission wavelength maxima for Cy5 are 649 nm and 670 nm respectively. LUM015 employs a fluorescent molecule with excitation and emission in the far red spectrum (< 700 nm wavelength) because in that range light can travel effectively through 1mm of tissue and tissue autofluorescence is minimal, allowing higher sensitivity due to lower background [11].

**Figure 1:** Schematic representation of LUM015.

Cathepsins are a family of enzymes that are involved in the degradation of the extracellular matrix to allow tumor growth and progression. These enzymes are upregulated in most human cancers and are also present in tumor associated macrophages at the tumor's invasive front [12-16]. Platt et. al. showed 60-fold higher cathepsin activity in breast cancer tissue than in healthy breast tissue [17]. Others report over-expression of cathepsin enzymes (B, K, L and D) in ductal carcinoma *in situ* as well as in invasive carcinomas (lobular and ductal) [13, 17-20]. Also, cathepsin B is typically over-expressed in inflammatory breast cancer, one of the most lethal forms of primary breast cancer. [21, 22]. The peptide sequence used in LUM015 is a pan-cathepsin substrate meaning that it will be cleaved by multiple enzymes of the cathepsin family. Because high activity of cathepsin enzymes is found in tumor cells and tumor associated macrophages surrounding the tumor at the invasive front, these enzymes provide an excellent marker for activating LUM015 at the tumor margin. The fluorescence of LUM015 is then detected with the LUM Imaging System

LUMICELL CONFIDENTIAL

[figure not shown]
This document is confidential. Do not disclose or use except as authorized.

to identify cancer and cancer-related cells for immediate resection and to distinguish them from adjacent normal tissue.

#### 4.4 LUM Imaging Device

The LUM Imaging Device consists of a computer control unit, monitor and light source mounted on a cart, and a hand-held optical head (LUM002/LUM003 imaging head). The computer control unit collects, analyzes (based upon Luminell's detection algorithm) and displays the resulting images gathered by the imaging head in real-time. The light source provides the illumination to excite the fluorescent dye present in LUM015. Light is transferred from the light source to the imaging head using an optical fiber bundle. The imaging head (**Figure 2**) was designed as a lightweight hand-held tool with a small profile to allow easy maneuverability and limited intrusiveness in the operating room. Because incisions and lumpectomy cavities can vary in size, Luminell offers two options for the distal end diameter: LUM002, which has a 2.6 cm field of view along with a 3.1 cm outer diameter and LUM003, which has a 1.3 cm field of view and a 1.9 cm outer diameter. The surgeons will be able to choose which device size to use for any given surgery. These two device options were proven to be optically equivalent when imaging freshly excised breast tissue. Both imaging heads have a 45° bend at the distal end for examination of the walls of the lumpectomy cavity.

The hand-held optical head will be used within the sterile surgical field. Consequently, a sterile barrier assembly will be provided to cover the optical head, which comes into contact with both the surgeon and the patient's exposed tumor bed. The sterile barrier assembly is installed on the LUM Optical Head in the OR using aseptic procedures.

[figure not shown]
**Figure 2:** (Left) Photo of the LUM 2.6 Imaging System. (Right) Rendering of the LUM002 Optical Head scanning a lumpectomy cavity. The sterile cover over the device is not shown.

#### 4.5 LUM decision software

LUMICELL CONFIDENTIAL

This document is confidential. Do not disclose or use except as authorized.

The LUM Imaging System is powered by Lumicell's proprietary decision software. The decision software uses an initial set of images acquired from the lumpectomy cavity after the main specimen is removed to set the tumor detection threshold. Then, while the surgeon scans the lumpectomy cavity walls with the LUM Optical Head, the decision software compares the intensity of an image against the tumor detection threshold and identifies whether a region of the image is suspected to contain tumor. Regions with fluorescence signal above the threshold are highlighted in the computer monitor for the surgeon to see in real-time; that is, there is no delay between the scanning of a region and the display of the results from that region. **Figure 3** shows the user interface and what the surgeon sees during scanning of the cavity walls. The decision software was developed and optimized during Phase A and Phase B of the Feasibility Study in breast cancer patients.

**Figure 3:** Screen shot of the user interface for the LUM decision software. Regions highlighted in red indicate areas suspected to have tumor.

## 5 STUDY DESIGN

### 5.1 Overview and background

Phase A and Phase B of the Feasibility Study were conducted at the Massachusetts General Hospital (MGH). Data from these studies were used to develop the Lumicell tumor detection algorithm that is implemented in the Lumicell decision software. Phase A included 5 subjects not injected with LUM015 for assessment of tissue autofluorescence and 10 subjects receiving LUM015 (5 subjects at a dose of 0.5 mg/kg and 5 subjects at a dose of 1.0 mg/kg) to assess the ability to distinguish LUM015 from autofluorescence. Phase A concluded with the analysis of the data to (1) assess patient safety, (2) determine initial parameters for the tumor detection algorithm and (3) select the dose of 1.0 mg/kg for Phase B. In Phase B, the tumor detection algorithm was fine-tuned for in vivo detection of residual cancer to guide the resection of additional shaved cavity margins (SCMs), known as therapeutic shaves. There were zero false negatives in the margin cavity and two second surgeries were avoided because the surgeon removed additional shaves guided by the LUM Imaging System that converted a positive margin into a negative one. The detailed results are presented in the Phase B Report.

Two of the three surgeons participating in Phase B requested an optical head with a smaller diameter because the incisions they typically make are too small for the optical head with a 3.1 cm outer diameter to fit. For Phase B, these two surgeons opted to make a larger incision than usual to fit the LUM Optical Head. In response to this request, Lumicell designed and built a smaller

LUMICELL CONFIDENTIAL

This document is confidential. Do not disclose or use except as authorized.

diameter distal end for the LUM Optical Head; however, the smaller version was not used in Phase B because the study was completed prior to obtaining IRB approval for using this version of the LUM Optical Head in the operating room.

We also refined our training process to highlight information that surgeons found important for using the LUM Imaging System comfortably and as intended. Examples of areas addressed during user training include: (1) making sure that the device is in contact with the tissue being scanned, (2) translating the region identified by the decision software as having cancer into the actual location of the shave to be removed once the LUM Optical Head is out of the cavity, (3) ensuring that the naming of the therapeutic shaves for pathology analysis matches the naming of the Luminicell images, and (4) selecting the proper size of the LUM Optical Head to be used for a given surgery.

The primary objective of this Phase C study is to further refine and verify the algorithm used for detection of residual cancer tissue. The secondary objective is to implement learning from Phases A and B of the Feasibility Study at MGH, in particular, training of breast cancer surgeons and hospital staff at the different sites. We are planning to include up to 20 sites participating in Phase C with approximately 1-3 surgeons at each site. In Phase C, a uniform method for orienting and inking the main specimen will be implemented prior to the subsequent pivotal study (see Appendix B).

## 5.2 Definitions

### 5.2.1 Definition of positive margins

For this protocol, positive margins are defined using the latest consensus from the Society of Surgical Oncology as follows:

- For invasive cancer with or without associated carcinoma in situ: cancer cells present on ink [1]
- For pure DCIS lesions: DCIS present within 2 mm from the inked surface [2]

### 5.2.2 Definitions of excised tissue

- **Main specimen:** also known as the “lump” or main mass, refers to the primary piece of tissue removed during a lumpectomy. Typically, this is the largest piece of tissue removed and it is intended to contain most of the tumor.
- **Shaved cavity margins (SCM):** thin pieces of tissue removed from the lumpectomy cavity walls after the main specimen is removed. In this study, we define three different types of SCMs below.
  - **Selective shaves:** shaved cavity margins removed from a specific location of the lumpectomy cavity wall based on intraoperative analysis of the main specimen by methods including, but not limited to, frozen sections, X-ray imaging, ultrasound imaging, palpation or visual examination.
  - **Comprehensive shaves:** shaved cavity margins removed from *all* surfaces of the lumpectomy cavity walls after resection of the main specimen.

LUMICELL CONFIDENTIAL

This document is confidential. Do not disclose or use except as authorized.

- **Therapeutic shaves:** shaved cavity margins removed using the guidance of the LUM Imaging System.

### 5.2.3 Definition of standard of care breast conserving surgeries

Breast conserving surgeries vary between surgeons and institutions. Table 1 outlines surgical procedure options that will be allowed in this study.

Table 1: Surgical procedures included in Phase C of the Feasibility Study.

SOC procedure	Description	Basis for final margin assessment
A. Main specimen	Main specimen is removed and some selective shaves may be removed based on, but not limited to, palpation, X-ray imaging, visual inspection of the intact main specimen . Selective shaves guided by sectioning of the main specimen are not included as part of this procedure (see B below).	Inked surface of main specimen
B. Main specimen followed by selective cavity shaves guided by analysis of main specimen sections	After procedure A above, additional selective shaves are removed based on analysis of sections from the main specimen , typically by X-ray imaging	The outermost inked surface for each orientation whether it is from the main specimen or the selective cavity shaves.
C. Main specimen followed by comprehensive cavity shaves	After procedure A above, a cavity shave is removed from all the available orientations. A shave from anterior or posterior may not be removed if no breast tissue remains at these surfaces.	Inked surface of the comprehensive cavity shaves.

[figure not shown]

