#### 5.4.3 Final margin assessment

Final margin assessment for a given orientation is done on the outermost surface resected for that specific orientation (see **Figure 5**). This surface could be on the main specimen, the SOC shaves or the therapeutic shaves. All the resected tissue will be handled and processed for margin assessment following the institution's current practices for breast conserving surgeries.

LUMICELL CONFIDENTIAL

This document is confidential. Do not disclose or use except as authorized.

**Figure 5:** Final margin assessment for a given orientation is based on the outermost surface resected (marked in red in the sketch). For the example in the sketch, final margin assessment for the medial orientation is based on pathology of the main specimen. Final margin assessments for the lateral orientation is based on the therapeutic shave. Final margin assessment for the superior orientation is based on the selective or comprehensive shave. Final margin assessment for the inferior orientation should be based on the therapeutic shave.

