3.4 Other analyses (secondary endpoints in pivotal study)

This endpoint is defined as:

- Proportion of patients with positive-margins after standard of care breast-conserving surgery who have a LUM Imaging System signal in the cavity above the threshold as defined by the tumor detection algorithm (i.e., a positive LUM signal). The endpoint is estimated as:

$$\frac{\# \text{ positive margin patients after SOC with LUM signal above the threshold}}{\# \text{ positive margin patients after SOC}}$$

- Proportion of subjects with pathology-positive margins after standard of care breast-conserving surgery, for whom additional therapeutic shaves resulted in pathology-negative margins. Note: This efficacy metric also estimates the potential reduction in re-excision surgeries following standard of care breast-conserving surgery that resulted from a positive SOC margin. This is estimated as:

$$\frac{\# \text{ positive margin patients after SOC with all final negative margins after the LUM procedure}}{\# \text{ positive margin patients after SOC}}$$

- Mean absolute volume (cc) of tissue removed from therapeutic shaves. For each subject, absolute shave volume will be calculated as length (c) \times width (c) \times depth (c) for each therapeutic shave with the sum by subject of all therapeutic shaves. Dimensions for the tissue will be obtained as entered in the case report form from the standard of care pathology report. Subjects with no therapeutic shaves taken will have a therapeutic shave volume of 0cc. The proportion of the subjects with and without therapeutic shaves will be reported. The mean and median (with 90% confidence interval) of the total surgery volume of tissue excised and total volume of the SOC tissue will be reported grouped by the subjects with or without therapeutic shaves.

LUMICELL CONFIDENTIAL

This document is confidential. Do not disclose or use except as authorized.

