- l. For reported microinvasive cancer, adjudicated correction will be provided external to the eCRF and will be used to change the margin type from Invasive to DCIS following NCCN guidelines.
- m. Margins for SOC and final margins will be derived from the tumor distance to margins. If there is a discrepancy between the derived margins based on distance and the margin status determined by the clinical site (could be due to different criteria used by the clinical sites), adjudication of the margin status will be done by Luminicell based protocol defined margin criteria (section 3.1).

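### Table 1 row A reads the margin on the main specimen even when selective shaves were taken, against row B and section 5.4.3, and the SAP does not say which surface defines margin status after standard of care

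*Protocol*

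**What the plan says.** Protocol 5.2.3, Table 1, lists three SOC procedures with a basis for final margin assessment for each. Row A states that "some selective shaves may be removed based on, but not limited to, palpation, X-ray imaging, visual inspection of the" intact specimen, and gives as its basis "Inked surface of main specimen". Row B starts from procedure A, adds shaves guided by sections of the specimen, and uses "The outermost inked surface for each orientation whether it is from the main specimen or the selective cavity shaves".

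Protocol 5.4.3 gives the general rule: "Final margin assessment for a given orientation is done on the outermost surface resected for that specific orientation". It adds: "This surface could be on the main specimen, the SOC shaves or the therapeutic shaves". It makes no exception for procedure A.

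SAP 3.4 has two proportions whose denominator is patients with a positive margin after SOC: those with a LUM signal above threshold, and those converted to negative margins. The text of the conversion endpoint describes subjects "for whom additional therapeutic shaves resulted in pathology-negative margins". The numerator of its formula counts "positive margin patients after SOC with all final negative margins after the LUM procedure".

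SAP 4.8.3, item m, says: "Margins for SOC and final margins will be derived from the tumor distance to margins". It does not name the surface from which the distance is taken. Protocol Table C1 gives tissue removed after inspection of the intact specimen the label Additional, in a separate row from SOC shaves.

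**The concern.** A selective shave taken under procedure A can clear a main-specimen margin that was positive. Under row A that orientation is still positive. Under row B or 5.4.3 it is negative. The documents therefore give two answers for the same tissue.

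The choice affects three quantities in the SAP: the denominators of the two proportions in 3.4, the conversion numerator, and the inferred truth in 3.3.2, which falls back on the margin of the prior resected tissue when an orientation has neither a shave nor a re-excision. SAP 3.4 also presents the conversion proportion as an estimate of the potential reduction in re-excision surgery. SAP section 1 says the analyses follow the proposed pivotal endpoints, and Protocol 15.5 says that the combined algorithm training data from Phases B and C will be used to power the pivotal trial. An error in either direction would matter to a reader of those results.

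**Working it through.** **Step 1. The rules side by side**, for one orientation with a positive main-specimen margin and a clear selective shave taken before LUM imaging:

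| Rule | Surface read | Status |
|---|---|---|
| Table 1 row A | main specimen | positive |
| Table 1 row B | outermost of main specimen and selective shave | negative |
| Protocol 5.4.3 | outermost surface resected | negative |

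Row B begins where procedure A ends. Taken literally, then, the procedure A shave counts only if the operation goes on to procedure B.

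**Step 2. Does the SAP settle it?** Item m of 4.8.3 names tumor distance but no surface. Item g of 4.8.3 treats SOC shaves as part of the margin analysis, but covers only those taken after LUM imaging. The SAP does not cite Table 1 and does not say whether Additional tissue counts toward SOC status. The point is left open.

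**Step 3. Effect on the conversion proportion.** The documents give no counts, so these are assumptions:
- m: patients SOC-positive on the outermost surface
- c: those truly converted by therapeutic shaves
- k: procedure A patients positive on the main specimen only, cleared by their own selective shave, with all final margins negative on the outermost surface

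Formulas:
- 5.4.3 for both SOC and final status: c/m
- row A for SOC status, 5.4.3 for final status: (c+k)/(m+k)
- row A for both, with therapeutic shaves still credited: c/(m+k)

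The second exceeds the first by k(m−c)/[m(m+k)], which is positive whenever c is less than m and k is above zero. With m = 20 and c = 4:

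| k | 5.4.3 for both | Row A then 5.4.3 | Row A for both |
|---|---|---|---|
| 1 | 4/20 = 20.0% | 5/21 = 23.8% | 4/21 = 19.0% |
| 2 | 20.0% | 6/22 = 27.3% | 4/22 = 18.2% |
| 5 | 20.0% | 9/25 = 36.0% | 4/25 = 16.0% |
| 10 | 20.0% | 14/30 = 46.7% | 4/30 = 13.3% |

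The last column is generous to row A, which strictly read would not credit therapeutic shaves either.

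**Step 4. Effect on the LUM-signal proportion.** Assume 16 of 20 SOC-positive patients (80%) have a signal, and that a fraction f of the k cleared patients do. Using row A for SOC status gives (16+kf)/(20+k):
- k = 2: 16.2/22 = 73.6% at f = 0.1, and 17/22 = 77.3% at f = 0.5
- k = 5: 16.5/25 = 66.0% at f = 0.1, and 18.5/25 = 74.0% at f = 0.5

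Under these assumptions the change is against the device. Similarly, if the main specimen were taken as the inferred truth in SAP 3.3.2, a LUM-negative orientation that had been cleared would change from a true negative to a false negative, and sensitivity would fall.

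**Step 5. What does not depend on this.** The expected enrollment in Protocol 15.2 reproduces as 32/(19/40) = 67.4, against the stated 67. It uses no margin status.

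**The case against.** The strongest reply is that inflation needs two rules combined, and no passage combines them. The Table 1 column is headed as the basis for final margin assessment, and does not define positive after SOC. If row A governs final status, the cleared patient stays positive and is no conversion. If 5.4.3 governs, she never enters the denominator. The SAP derives both statuses in the same way, and the text of the conversion endpoint excludes a patient whose margin was not cleared by a therapeutic shave. The prior resected tissue in SAP 3.3.2 most naturally means the selective shave where one exists. Row C is loose too, since it names only the comprehensive shaves although an anterior or posterior shave may be missing. The column may be shorthand.

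Most of this stands. A reader might infer that the plan does count margins already cleared by standard care as LUM conversions. The documents do not support that. A reader might also infer that any error favors the device, and step 4 shows otherwise.

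The reply does not remove the contradiction. Table 1 lists only SOC tissue and no therapeutic shaves, so reading it as the margin at the end of SOC is natural, with 5.4.3 as the margin after LUM. The conversion formula, unlike its text, requires no therapeutic shave, so it would not stop a cleared patient from being counted.

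**Conclusion.** Row A contradicts row B and Protocol 5.4.3 for any orientation in which a procedure A selective shave was taken, and the SAP does not resolve the conflict. Followed literally, row A misclassifies an orientation that the selective shave had already cleared. This should be reconciled before analysis.

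The direction and size of any bias depend on how the rules are applied. Row A followed by 5.4.3 inflates conversion, from 20.0% to 27.3% at m = 20, c = 4, k = 2. Row A throughout understates it, at 18.2%. Under either use, the LUM-signal proportion and sensitivity could move against the device. All these counts are assumed: the documents do not report how many procedure A patients have a cleared main-specimen margin, and if none do, nothing changes. Some figures, including SAP Figure 3 on the prior margin, are not available here and could show the intended reading.

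The SAP states that the protocol had no hypothesis-tested endpoints, so no error rate or power is affected.

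**What to change.** 1. In Protocol Table 1, reconcile row A with 5.4.3 by giving it the row B basis.
2. In SAP 3.4 and 4.8.3, state that for analysis, SOC margin status is read per orientation on the outermost surface resected before LUM imaging, for all procedure types, and that Additional tissue and selective shaves are included. Keep item g of 4.8.3 as the stated rule for SOC shaves taken after imaging.
3. In SAP 3.4, align the conversion formula with its text by requiring a therapeutic shave in each orientation counted as converted.

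The cost is one table cell and two or three sentences. The changes concern classification for analysis and should need no new data, provided margin distances are recorded for each piece of tissue. The reported conversion proportion may be lower than under the formula as it stands.
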